Appendix D10b: Exploratory Bayesian analysis for lactate clearance	43

1. Introduction

This document is the Statistical Analysis Plan (SAP) for the RePHILL trial, and should be read in conjunction with the current trial protocol. This SAP details the proposed analyses and presentation of the data for the main paper(s) reporting the results for the RePHILL trial.

The results reported in these papers will follow the strategy set out here. Subsequent analyses of a more exploratory nature will not be bound by this strategy, though they are expected to follow the broad principles laid down here. The principles are not intended to curtail exploratory analysis (e.g. to decide cut-points for categorisation of continuous variables), nor to prohibit accepted practices (e.g. transformation of data prior to analysis), but they are intended to establish rules that will be followed, as closely as possible, when analysing and reporting data.

Any deviations from this SAP will be described and justified in the final report or publication of the trial (using a table as shown in Appendix A). The analysis will be carried out by an appropriately qualified statistician, who should ensure integrity of the data during their data cleaning processes.

2. Background and rationale

The background and rationale for the trial are outlined in detail in the protocol. In brief, the administration of high ratios of plasma to packed red blood cells (PRBC) has been widely adopted for in-hospital treatment of major traumatic haemorrhage. Acceptance of in-hospital haemostatic resuscitation saw the British military implement it for battlefield casualty retrieval. With the increasing adoption of giving Pre-Hospital Blood Products (PHBP) for trauma in both the UK and abroad, in both military and civilian settings, it is important to determine whether this intervention is effective. The provision of PHBP requires considerable logistical and financial resources and RePHILL will establish a high quality evidence base for PHBP resuscitation.

3. Trial objectives

The primary objective is to investigate the clinical effectiveness of PHBP resuscitation compared to the current standard care of restricted crystalloid based resuscitation in participants suffering from major traumatic haemorrhage.

Secondary objectives are to test the hypotheses that, when compared to standard care, does PHBP resuscitation:

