- I. Improve blood pressure, heart rate and capillary oxygenation on Emergency Department (ED) arrival?
- II. Prolong on-scene time?
- III. Reduce pre-hospital fluid requirements?
- IV. Reduce in-hospital transfusion requirements?

- V. Reduce trauma-induced coagulopathy?
- VI. Preserve platelet function?
- VII. Lead to a greater incidence of transfusion-related complications, particularly acute respiratory distress syndrome (ARDS)?
- VIII. Lead to blood product wastage?
- IX. Affect haemoglobin concentration levels on ED arrival?

4. Trial methods

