4.4. Secondary outcome measures

Secondary outcomes are as follows:

- Individual components of the primary outcome
- All-cause mortality within 3 hours of randomisation
- All-cause mortality within 30 days of randomisation
- Pre-hospital time and type and volume of fluid
- Vital signs (systolic blood pressure, heart rate, capillary oxygen saturation) at scene, on arrival at the ED, then also at 2, 6, 12 and 24 hours after arrival at ED
- Haemoglobin concentration on ED arrival

- (Venous) lactate concentration on arrival at ED and at 2 hours after arrival at ED
- Trauma-induced coagulopathy (defined as International Normalised Ratio (INR) >1.5) to be measured on arrival at ED, and also at 2 and 6 hours after arrival at ED
- Total blood product receipt at 6, 12 and 24 hours after arrival at ED
- ARDS within the first 7 days after injury
- Transfusion-related complications
- Organ failure-free days The presence of organ failure is defined as any Sequential Organ Failure Assessment (SOFA) component score of ≥ 3 . Organ failure will be assumed to be absent if the participant is discharged from acute care and will be assumed to be present if the participant has died

At selected receiving hospital sites (RHS) the following secondary outcomes will also be recorded:

- Coagulation measured viscoelastically by rotational thromboelastometry (ROTEM[®])
- Platelet function using multiple electrode impedance aggregometry (MultiPlate)

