4.7. Sample size

Although no definitive data exists on the composite primary outcome measure, observational studies suggest potentially dramatic reductions in mortality from civilian pre-hospital PRBC¹ and military pre-hospital PRBC with thawed plasma². Following extensive consultation with experts in pre-hospital trauma resuscitation, it is considered that an absolute reduction of 10% in the proportion of participants experiencing one of the component primary outcomes is clinically meaningful for the participants and is an appropriate effect size upon which to base the power calculation.

To detect an absolute difference of 10% between groups in the proportion of participants experiencing either episode mortality or lactate clearance $<20\%/h$ in the two hours post-randomisation (i.e. from 20% in the standard care group to 10% in the group receiving PHBP) using the method of difference between proportions (2-sided Fisher's Exact Test) with 80% power, and a type 1 error rate of 5% (i.e. $\alpha=0.05$), requires 219 participants per group to be randomised, 438 participants in total. Assuming and adjusting for a 10% loss to follow-up rate, 490 participants will need to be recruited.

The interim analysis for the Data Monitoring Committee (DMC) meeting in May 2018 reported the results on the 192 participants recruited by 20th April 2018. A pooled event rate of 65% experiencing either episode mortality or lactate clearance $<20\%/h$ in the two hours post-randomisation was observed in these participants. This observed rate does not correspond with the pooled event rate of 15% assumed in the original sample size calculations. On the DMC's recommendations, this issue was discussed with the TSC in October 2018. The TSC recommended that the power calculations were framed in terms of a relative risk rather than an absolute risk, with the original target sample size of 490 unchanged.

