6.2. Baseline characteristics
The trial population will be tabulated as per Appendices D2, D2a and D2b. Categorical data will be summarised by number of participants, counts and percentages. Continuous data will be summarised by the number of participants, mean and standard deviation if deemed to be normally distributed or number of participants, median and interquartile range if data appear skewed, and ranges if appropriate. Tests of statistical significance will not be undertaken, nor confidence intervals presented. ⁸
7. Interventions

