Appendix D2a: Prehospital timeline by group

The duration in minutes between the time of the 999 call and prehospital events. Values above the diagonal correspond to the PHBP group and values below the diagonal correspond to the Crystalloid group.

Prehospital event	999 Call	On-scene attendance	Randomisation Capillary Lactate	Treatment box opening	Left Scene*	Arrival at ED**
999 call		Median (IQR) (n N)	Median (IQR) (n N)	Median (IQR) (n N)	Median (IQR)	Median (IQR)

					(n N)	(n N)
On-scene attendance	Median (IQR) (n N)		Median (IQR) (n N)	Median (IQR) (n N)	Median (IQR) (n N)	Median (IQR) (n N)
Randomisation Capillary Lactate	Median (IQR) (n N)	Median (IQR) (n N)		Median (IQR) (n N)	Median (IQR) (n N)	Median (IQR) (n N)
Treatment box opening	Median (IQR) (n N)	Median (IQR) (n N)	Median (IQR) (n N)		Median (IQR) (n N)	Median (IQR) (n N)
Left Scene*	Median (IQR) (n N)	Median (IQR) (n N)	Median (IQR) (n N)	Median (IQR) (n N)		Median (IQR) (n N)
Arrival at ED**	Median (IQR) (n N)	Median (IQR) (n N)	Median (IQR) (n N)	Median (IQR) (n N)	Median (IQR) (n N)	

*Added in v4.0 of pre-hospital CRF (active in all sites from 29th August 2019)

**These numbers are lower than the totals of randomised participants due to deaths on-scene or during transit to hospital.

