Appendix D7: Secondary outcomes results

Outcome	Time-point	PHBP (N=)	Crystalloid (N=)	Adjusted treatment effect and 95%CI	p-value
Episode Mortality ¹	Up to discharge from acute care	n/N (%)	n/N (%)	Relative risk (95% CI) ²	p-value
Episode Mortality ¹	Up to discharge from acute care	n/N (%)	n/N (%)	Absolute risk difference (95% CI) ³	
Failure to achieve lactate clearance ⁴	2 hours post-randomisation	n/N (%)	n/N (%)	Relative risk (95% CI) ⁵	p-value
Failure to achieve lactate clearance ⁴	2 hours post-randomisation	n/N (%)	n/N (%)	Absolute risk difference (95% CI) ⁶	
All-cause mortality	Within 3 hours of randomisation	n/N (%)	n/N (%)	Relative risk (95% CI) ⁷	p-value
All-cause mortality	Within 3 hours of randomisation	n/N (%)	n/N (%)	Absolute risk difference (95% CI) ⁸	
All-cause mortality	Within 3 hours of randomisation ⁹	n/N (%)	n/N (%)	Relative risk (95% CI) ⁷	p-value
All-cause mortality	Within 3 hours of randomisation ⁹	n/N (%)	n/N (%)	Absolute risk difference (95% CI) ⁸	
All-cause mortality	Within 30 days of randomisation	n/N (%)	n/N (%)	Relative risk (95% CI) ⁷	p-value
All-cause mortality	Within 30 days of randomisation	n/N (%)	n/N (%)	Absolute risk difference (95% CI) ⁸	
Pre-hospital time	Time to ED arrival from 999 call	(N ..) Mean (SD)	(N ..) Mean (SD)	Mean difference (95% CI) ¹⁰	p-value
Pre-hospital time	Time to ED arrival from randomisation	(N ..) Mean (SD)	(N ..) Mean (SD)	Mean difference (95% CI) ¹⁰	p-value
Pre-hospital fluid type and volume					
Type & Total volume of Fluids given prior to intervention	Prior to intervention up to ED arrival	(N ..) Mean (SD)	(N ..) Mean (SD)	Mean difference (95% CI) ¹¹	p-value
Type & Total volume of Fluids given post intervention	Post intervention up to ED arrival	(N ..) Mean (SD)	(N ..) Mean (SD)	Mean difference (95% CI) ¹¹	p-value
Vital Signs					
Systolic blood pressure	On-scene, ED arrival, 2, 6, 12, 24 hours after ED arrival	(N ..) Mean (SD)	(N ..) Mean (SD)	Mean difference (95% CI) ¹²	p-value
Diastolic blood pressure	On-scene, ED arrival, 2, 6, 12, 24 hours after ED arrival	(N ..) Mean (SD)	(N ..) Mean (SD)	Mean difference (95% CI) ¹²	p-value
Heart rate	On-scene, ED arrival, 2, 6, 12, 24 hours after ED	(N ..) Mean (SD)	(N ..) Mean (SD)	Mean difference (95% CI) ¹³	p-value

	arrival				
Capillary Oxygen Saturation	On-scene, ED arrival, 2, 6, 12, 24 hours after ED arrival	(N ..) Mean (SD)	(N ..) Mean (SD)	Mean difference (95% CI) ¹⁴	p-value

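### Secondary objective II is a hypothesis about on-scene time, but the SAP tests only intervals that end at ED arrival and shows on-scene time without an estimate or confidence interval

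*SAP*

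**What the plan says.** SAP section 3 introduces the secondary objectives with "Secondary objectives are to test the hypotheses that, when compared to standard care, does PHBP resuscitation", and item II in the list is "Prolong on-scene time". The corresponding entry in section 4.4 is "Pre-hospital time and type and volume of fluid", which names no on-scene interval.

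Appendix D7 turns that entry into two rows, "Time to ED arrival from 999 call" and "Time to ED arrival from randomisation", each with a mean difference, 95% CI and p-value. Footnote 10 to D7 confirms that both intervals end at ED arrival.

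The intervals ending at departure from scene, starting from on-scene attendance or from treatment box opening, appear only in Appendix D2a, as median (IQR) with n and N by group. Section 6.2 lists D2a with the baseline tables and says of them: "Tests of statistical significance will not be undertaken, nor confidence intervals presented". A D2a footnote on the departure time reads "Added in v4.0 of pre-hospital CRF (active in all sites from 29th August 2019").

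**The concern.** An objective stated as a between-group hypothesis should have an analysis that estimates the quantity it names. Objective II has none. The two tested intervals contain on-scene time but also other components:

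- **999 call to ED arrival** includes the response time and the scene time before the box is opened, neither of which the allocated treatment can affect. It also includes transport.
- **Randomisation to ED arrival** starts at box opening and is the closer proxy, but it still includes transport. Section 9.9 itself expects transport time to differ between air and ground.

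Departure from scene happens after the box is opened, which section 4.6 defines as the moment of randomisation. Box opening to departure is thus a post-randomisation outcome, yet it falls under a reporting rule written for baseline characteristics. If the SAP is followed as written, the report will hold no estimate of the difference in on-scene time and no interval showing how large a delay remains compatible with the data. A null result on time to ED arrival would not exclude a delay on scene.

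**Working it through.** The mismatch is textual, and no SAP figure has to be reproduced. The arithmetic below concerns only how many participants could contribute and what can be said about power.

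**1. The places side by side**

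| Place in SAP | Content | Inference on on-scene time |
|---|---|---|
| Section 3, II | Hypothesis on on-scene time | Called for |
| Section 4.4 | Pre-hospital time | Not named |
| Section 9.6 | Linear regression for continuous outcomes | Not named |
| Appendix D7 | Two intervals ending at ED arrival | None |
| Appendix D2a with 6.2 | Intervals to leaving scene, median (IQR) | Ruled out |

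**2. Ceiling on the number with a departure time**

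Section 4.7 gives the target of 490 and says the May 2018 interim analysis "reported the results on the 192 participants recruited by 20th April 2018". Assume that 490 are recruited and that CRF v4.0 was not in use before that date.

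- Without a departure time: at least 192/490 = 39%.
- With one: at most 490 − 192 = 298 (61%), or 149 per arm.

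This is a ceiling, because v4.0 was active at all sites only about 16.3 months later. As a rough indication, section 4.10 gives a 6-month pilot reviewed on 26 April 2017. If the full six months preceded the review, recruitment had run for at least 18 months by 20 April 2018, a rate of at most 192/18 = 10.7 per month. At that rate, with no early use of v4.0, a further 10.67 × 16.3 ≈ 174 participants predate it. That leaves about 298 − 174 = 124, or 62 per arm. The true number is not in the SAP.

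**3. Precision of a direct comparison**

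Difference detectable with 80% power at two-sided 5%, in SD units: (1.96 + 0.84) × √(2/n).

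| n per arm | Detectable difference |
|---|---|
| 245 | 0.25 SD |
| 149 | 0.32 SD |
| 100 | 0.40 SD |
| 75 | 0.46 SD |

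**4. Dilution in the tested intervals**

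Take an on-scene difference that would have 80% power at 245 per arm. Add an independent component that treatment does not affect, with SD r times the on-scene SD. The total SD grows by √(1 + r²), and power on time to ED arrival becomes:

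| r | Power |
|---|---|
| 0.5 | 71% |
| 1 | 51% |
| 1.5 | 34% |
| 2 | 24% |

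**5. Does the direct test have more power?**

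The SAP gives no SDs. Assume independent SDs of 10 (response), 15 (scene) and 15 min (transit), a true delay of 5 min, and all scene variation after box opening. Power = Φ(5/(SD × √(2/n)) − 1.96).

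| Interval | SD (min) | n per arm | Power |
|---|---|---|---|
| 999 call to ED | √(10² + 15² + 15²) = 23.5 | 220 | 61% |
| Randomisation to ED | √(15² + 15²) = 21.2 | 220 | 70% |
| Box opening to leaving scene | 15 | 149 (ceiling) | 82% |
| Box opening to leaving scene | 15 | 62 (rough indication) | 46% |

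The direct test breaks even with 999 call to ED at 220 × 225/550 = 90 per arm, and with randomisation to ED at 220 × 225/450 = 110 per arm. The ceiling is above both thresholds and the rough indication is below both, so the ranking cannot be settled from the SAP.

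**The case against.** The strongest reply is that on-scene time is not left out. D2a reports both relevant intervals by group with n and N in each cell, and it footnotes the late CRF field, so the restricted denominator is visible. D7 correctly implements the outcome that section 4.4 lists, which is pre-hospital time, and labels its intervals plainly. Nothing in the SAP tells a reader to interpret them as on-scene time. Randomisation to ED arrival already excludes the parts that treatment cannot influence before box opening, and it keeps the early participants. On this view one clarifying sentence would be enough.

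Much of this stands. The objective is answered descriptively, and randomisation to ED arrival is a reasonable proxy. Two stronger readings might be inferred and are not supported. One is that objective II is ignored altogether; D2a shows otherwise. The other is that a direct test on the participants with a departure time must have more power than the tested intervals. That follows only if the ceiling of 149 per arm is taken as the expected number and the SDs are assumed.

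The reply does not remove the gap between a hypothesis that section 3 says will be tested and a table for which section 6.2 forbids even a confidence interval. Nor does the SAP say that objective II is to be answered by proxy or only for later recruits.

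**Conclusion.** The point holds in a limited form. Objective II is stated as a hypothesis, but its quantity is only described, under a baseline rule that does not suit a post-randomisation interval. The intervals that are tested include transport. This affects one of nine secondary objectives and leaves the primary outcome untouched. It is a cheap improvement and not a threat to the trial's main conclusion.

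The mismatch rests on the SAP text alone. The ceiling of 298 assumes full recruitment and no use of CRF v4.0 before 20 April 2018. All SDs and the 5-minute delay are illustrative. No claim is made that the direct comparison is more powerful; the gain is an estimate, with its uncertainty, of the quantity the objective names.

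**What to change.** Add one row to Appendix D7 as the outcome for objective II: time from treatment box opening (randomisation) to leaving scene, as an IDS-adjusted mean difference with 95% CI, in participants with a recorded departure time. With it:

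- report N per arm;
- state how deaths on scene are handled, since these participants have no departure for the interval to end at;
- state that the comparison applies to participants recruited under pre-hospital CRF v4.0.

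Keep randomisation to ED arrival as the supportive analysis across the whole recruitment period, and keep 999 call to ED arrival as a pre-hospital time outcome. Say that neither is a test of on-scene time. The attendance-to-departure interval can stay descriptive in D2a, because it includes scene time before the box is opened.

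The cost is SAP wording and one table row, using data already collected for D2a. The downside is a smaller sample of unknown size, to which early participants do not contribute, so the confidence interval may be wide.

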4.6. Randomisation

Participants will be randomised at the level of the individual in a 1:1 ratio to either PHBP (Lyophilised Plasma LyoPlas N-w (LyoPlas) and PRBC) resuscitation or crystalloid (0.9% sodium chloride [normal saline]) resuscitation.

Randomisation will be performed centrally at the Birmingham Clinical Trials Unit (BCTU) using stratification by intervention delivery site (IDS) to account for variation in trauma care and type of trauma between delivery sites.

In the RePHILL trial, the blood banks will maintain a constant supply of randomised trial interventions to the Pre-Hospital Emergency Medical (PHEM) team. The blood bank will obtain the randomised allocations via a secure online system at the BCTU.

Blood banks will be supplied with pre-printed 'treatment box number' labels. A registered user at the blood bank will request a treatment allocation from the BCTU and will receive a treatment box number and treatment arm allocation. The allocated trial intervention will be packed into transport boxes affixing the correct labels. Transport boxes will be issued as a pair, one marked red and one marked yellow per single randomised allocation. The packed, sealed transport

boxes will be dispatched to the PHEM base using an established courier service as required

On-scene, the PHEM doctor will assess the potential participant's vital signs on scene and confirm if eligible for entry into the RePHILL trial. If they fulfil the eligibility criteria for the trial, the randomised treatment will be given. Participants are considered randomised into the trial when the PHEM team open the first transport box containing the allocated trial intervention.

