9.1. Covariate adjustment

In the first instance, intervention effects between groups for all outcomes will be adjusted for IDS (stratification variable; see section 4.6) as a fixed effect (this will be the primary analysis). A secondary analysis adjusting for IDS and the following prognostic variables (age, lactate, cardiac arrest and Glasgow Comma Score (GCS) at randomisation) as fixed effects will also be undertaken for the primary outcome measure (and the individual components).

For binary outcomes, if the log-binomial model fails to converge, a Poisson regression model with robust standard errors will be used to estimate the same parameters.⁹ If this also fails to converge, unadjusted estimates will be produced from the log-binomial model. It will be made clear in the final report why this occurred (e.g. not possible due to low event rate/lack of model convergence).

Longitudinal secondary outcomes (e.g. vital signs, venous lactate concentration, etc.) will also be adjusted for their baseline values.

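### On-scene vital signs, taken before randomisation, are listed as a tested outcome time point, against the plan's own rule for baseline data

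*SAP*

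**What the plan says.** Section 4.6 gives the order of events. On arrival, "the PHEM doctor will assess the potential participant's vital signs on scene and confirm if eligible for entry into the RePHILL trial". Randomisation comes afterwards: "Participants are considered randomised into the trial when the PHEM team open the first transport box containing the allocated trial intervention". Appendix D2 accordingly places the on-scene vital signs among the baseline characteristics, and section 6.2 says of the D2, D2a and D2b tables: "Tests of statistical significance will not be undertaken, nor confidence intervals presented".

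The same readings also appear as outcomes. Section 4.4 includes among the secondary outcomes "Vital signs (systolic blood pressure, heart rate, capillary oxygen saturation) at scene, on arrival at the ED", followed by the later hospital time points. Section 4.5 repeats on-scene as an assessment time for secondary outcomes. In Appendix D7 the time-point cell for systolic pressure, diastolic pressure, heart rate, oxygen saturation and respiratory rate reads "On-scene, ED arrival, 2, 6, 12, 24 hours after ED arrival", and each row has a mean difference with 95% CI and a p-value.

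On the model, section 9.1 says: "Longitudinal secondary outcomes (e.g. vital signs, venous lactate concentration, etc.) will also be adjusted for their baseline values". Section 9.6 names vital signs and pre-hospital fluid volume among the continuous outcomes, to be analysed by linear regression adjusted for IDS and baseline values.

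Appendix D7 also has a row labelled "Type & Total volume of Fluids given prior to intervention", again with a mean difference, CI and p-value. Its time-point cell, however, runs from before the intervention to ED arrival.

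**The concern.** A reading taken to decide eligibility cannot be changed by an allocation revealed when the box is opened. Any difference between the groups in on-scene vital signs is chance imbalance. Under D7 it would appear in the treatment-effect column, with footnotes that describe a positive difference as a higher value with PHBP. Section 5.2 makes no multiplicity correction, so a nominally significant row would stand beside the genuine post-randomisation comparisons without any marker.

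The plan also gives the analyst two incompatible instructions for one set of numbers: no test in D2, a test in D7. If the model in 9.1 and 9.6 is followed literally at this time point, it may not be estimable at all.

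The fluid row raises a related question. Its label describes something fixed before treatment; its window does not.

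**Working it through.** No stated sample-size, power or alpha figure underlies this point, so there is none to reproduce. The check sets the sections side by side and then examines what the specified model does.

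**1. Timing.** Section 4.6: vital signs are assessed, eligibility is confirmed, the box is opened, and that opening is randomisation. The on-scene readings are therefore pre-randomisation. D2 treats them so.

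**2. Which vital signs.** Section 4.4 names three (systolic pressure, heart rate, oxygen saturation). D7 has five, adding diastolic pressure and respiratory rate.

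**3. Which baseline.** Sections 9.1 and 9.6 adjust for baseline values without defining them for vital signs. The on-scene readings in D2 are the only pre-randomisation vital signs the SAP lists, so they are the natural covariate. This is an inference.

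**4. The model if the on-scene value Y0 is both response and covariate.**

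Y0 = a + b·group + (IDS terms) + d·Y0 + error

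Least squares is solved exactly by d = 1 with every other coefficient 0. The residual sum of squares is then 0, so the standard error of b is 0 and the test statistic is 0/0. A simulated check with n = 490, four sites and arbitrary normal data gave:

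| Quantity | Result |
|---|---|
| Coefficient of Y0 | 1.0 |
| R-squared | 1.0 |
| Residual sum of squares | 9 × 10⁻²⁶ |
| Treatment coefficient | 8 × 10⁻¹⁵ |

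The last two values are rounding error around zero. The algebra does not depend on the simulated distribution.

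**5. The model if the baseline term is left out at this time point.** Regression of Y0 on group and IDS alone is a valid test of a null that is true by design. Over 4,000 simulated trials it rejected in 4.9%, against the nominal 5%. For five such tests:

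- independent tests: 1 − 0.95⁵ = 1 − 0.774 = 0.226, about 23%;
- correlated tests, as vital signs from the same patients will be: lower, with 5% as the floor.

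Steps 4 and 5 are alternatives, and their consequences do not add.

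**6. The fluid row.** D7 pairs it with a post-intervention row whose window runs from the intervention to ED arrival. Read literally, the first row's window contains the second's, so the first would be total pre-hospital fluid. Read by its label, it stops at the intervention. The document does not settle which is meant.

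**The case against.** The strongest defence is that D7 is a compressed reporting template. Each vital-sign row puts six time points in one cell, with a single placeholder for the effect and another for the p-value. Read with D2 and section 6.2, the on-scene value could simply be the descriptive starting point of a longitudinal series, and a sensible analyst might leave its test cell empty. That is possible, but the document does not say it. No footnote exempts the on-scene time point, and section 4.4 names it as an outcome time in the body text. D7 elsewhere omits the p-value where none is wanted, in the absolute-risk-difference rows and the exploratory rows. Lactate is handled as one would expect: the randomisation value is in D2, and only later values are in D7.

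Other parts of the defence stand, and they limit what can be claimed. A reader might infer any of the following, none of which the SAP supports:

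- *The plan states that it regresses the baseline on itself.* It does not; this depends on step 3 of the working.
- *Pre-intervention fluid is a sixth test that is null by design.* Its printed window reaches ED arrival. If that is what was meant, it is total pre-hospital fluid and a proper outcome under Objective III, so it cannot be counted with the five.
- *Section 6.2 forbids testing the fluid row.* That rule covers the D2 tables, and fluids are in none of them.
- *On-scene differences would be reported as answering Objective I.* That objective concerns values on ED arrival only.
- *Software output at this time point would mislead.* A package may print a tiny p-value from the degenerate model, but that is a ratio of rounding errors and an analyst should notice it.

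**Conclusion.** The point holds for on-scene vital signs. They are pre-randomisation data, shown as baseline in one table and given an effect estimate, interval and p-value in another, contrary to section 6.2. The comparison has no useful form: it is undefined if the on-scene value is the covariate, and otherwise it tests chance imbalance at 5% per test, with about 23% as the chance of at least one false positive in five under independence and less under correlation. The first branch assumes that the on-scene reading is the intended baseline.

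For the fluid row, the established fault is a contradiction between label and window. Whether it is also a test of pre-treatment data depends on how that is resolved.

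Only secondary outcomes are involved. The post-randomisation vital-sign comparisons, the primary analysis and the sample size are unchanged. The correction should be made because the analysis is wrong as written, but it does not threaten the trial's main conclusion.

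**What to change.** 1. In section 4.4 (three vital signs) and Appendix D7 (five), remove on-scene as a tested time point, or keep it with a footnote that it is descriptive only, with no effect estimate, CI or p-value. Align section 4.5.
2. In sections 9.1 and 9.6, state that the on-scene value is the baseline covariate for vital signs at ED arrival and later.
3. In D7, reconcile the label and window of the pre-intervention fluid row. If the quantity truly ends at the intervention, report it descriptively without estimate, CI or p-value; only then may it serve as the baseline covariate for post-intervention volume. If the window to ED arrival is what was meant, correct the label and do not use it as a covariate, because it would include post-randomisation fluid and overlap the outcome.

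The cost is SAP wording and table shells. No data collection, sample-size or power figure changes, and fewer p-values are reported.
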